7.3.4 Definitions for Criteria of Relatedness of Adverse Events to Device

Unrelated: The timing of the clinical event to the product administration makes a causal relationship not possible, or, other drugs, therapeutic interventions or underlying conditions provide a strong explanation for the observed event. Alternatively, common medical knowledge makes causal relationship implausible.

Unlikely Related: The timing of the clinical event to the product administration makes a causal relationship unlikely, or, other drugs, therapeutic interventions or underlying conditions provide a sufficient explanation for the observed event. Alternatively, common medical knowledge makes causal relationship unlikely.

Possibly Related: The timing of the clinical event to the product administration makes a causal relationship equally likely or not likely, and, other drugs, therapeutic interventions or underlying conditions provide only a low probability explanation for the observed event.

Probably Related: The timing of the clinical event to the product administration makes a causal relationship probable, and, other drugs, therapeutic interventions or underlying conditions do not provide a sufficient explanation for the observed event

Definitely Related: The timing of the clinical event to the product administration makes a causal relationship certain and common medical knowledge makes causal relationship highly probable.

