2.3 Safety Outcomes

Safety will be evaluated by:

- 1. Incidence of device-related, procedure-related and therapy- related adverse events
- 2. Incidence of device-related or unrelated serious adverse events, including unanticipated adverse device effects
- 3. Development of adverse eating behaviors as measured by EDE and QEWP-R

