7.1.2 Risks Associated with Stomas/ Fistulas and A-Tube

Risks related having a fistula/ stoma include: 1) abdominal discomfort/pain, 2) peristomal skin irritation/ inflammation, erythema and granulation tissue formation, 3) peristomal leakage and/or bleeding, 4) infection, 5) buried bumper syndrome and gastric erosion, 6) difficulty sleeping on abdomen,

reduced range of motion at the torso, 7) persistent fistula after tube removal, and 8) scarring and/or skin depression after tube removal.

Abdominal Discomfort/Pain. It is normal for subjects to have abdominal discomfort after endoscopic A-tube (or PEG tube) insertion, which subsides over several weeks. Subjects will be instructed to take over-the-counter pain medications such as acetaminophen as needed for 1 week after A-Tube placement. In addition, at discharge from the endoscopy suite, subjects will be given a 1-week prescription for pain medications that can be used to control abdominal discomfort. Supplementary pain medication will also be provided at the physician's discretion. The experience from the Feasibility Study found that musculoskeletal or neuropathic complaints (e.g. burning, pulling) after tube placement was effectively treated with general oral pain medications and/or medications for neuropathic pain. It was thought by the Sponsor and the Study Team that discomfort after the first few weeks was primarily associated with the "old" A-Tube design (e.g., ePTFE tube with helical ridges of exterior or tube). With the new A-Tube design implemented in September 2011, subjects report significantly greater comfort.

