7.3.1 Adverse events (AE)

The definitions of an Adverse Event and a treatment-emergent adverse event are as follows:

Adverse event (AE): any untoward, noxious, or unintended event experienced by a subject in a clinical trial of an investigational device, whether considered related to that investigational device or not. This definition also encompasses: 1) events that result from abuse of the device, 2) symptoms reported by the subject, 3) signs detected by the investigator or other competent observer, and 4) medically important deviations from normalcy in the results of ancillary investigations.

Treatment-emergent adverse event: an AE that is new in onset or aggravated in severity or frequency following placement of the investigational

device. This includes any change from baseline physical examination findings or results of diagnostic procedures (e.g., laboratory test, ECG, X-ray) that is clinically significant, i.e., requires diagnostic or therapeutic intervention beyond confirmation alone; however, such a finding shall not be recorded as a separate AE if it is intrinsic to, or results in, a clinical diagnosis that is recorded as an AE.

a. Anticipated Adverse Device Effects

The following events have been identified as possible (anticipated) adverse events that could be related to A-Tube implantation and use:

- 1) Risks of endoscopic placement of the A-Tube, as outlined in Section 7.1.1, are examples of procedure-related adverse events.
- 2) Risks related to the presence of the A-Tube, as outlined in Section 7.1.2, are examples of device-related adverse events.
- 3) Risks of Aspiration Therapy, as outlined in Section 7.1.3, are examples of therapy-related adverse events.
- 4) Behavioral Risks, as outlined in Section 7.1.4, are examples of therapy-related adverse events.
- 5) Risks related to concomitant drug therapy, as outlined in Section 7.1.5, are examples of study-related concomitant medication-related adverse events.
- 6) Risks of weight loss include gallstone formation, bone demineralization, alopecia, dehydration, changes in bowel habits, and loose skin are examples of therapy-related adverse events.

If the subject is female, the procedure may involve unforeseeable risks to an embryo or fetus should the subject become pregnant.

Anticipated adverse events that are NOT deemed serious adverse events need only be recorded on the CRF.

b. Unanticipated Adverse Device Effects

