Unanticipated adverse device effects (UADE) are defined as "any *serious* adverse effect on health or safety or any life-threatening problem or death caused by, or associated with, a device, if that effect, problem, or death was not previously identified in nature, severity, or degree of incidence in the investigational plan or application (including a supplementary plan or application), or any other unanticipated *serious* problem associated with a device that relates to the rights, safety, or welfare of subjects'

All unanticipated adverse events and deaths must be reported by telephone and in writing immediately, or within 48 hours of knowledge of the event, to Aspire Bariatrics. The PI must also inform the relevant Institutional Review Board, Medical Ethics Committee or similar body, if applicable, per local regulations.

The telephone report must be followed by a written report that is emailed or faxed to the Sponsor within two days to include the date of occurrence, complete description of the event, severity, duration (when appropriate), action taken, outcome, and the investigator's assessment of relatedness to the endoscopic procedure or the presence of the A-Tube. The incident shall also be recorded in the CRF on the Adverse Event Form.

c. Serious Adverse Event (SAE)

Serious adverse event (SAE): any AE that is fatal, immediately lifethreatening (i.e., presents an immediate risk of death at the time of the AE, not an AE that hypothetically might have caused death if it were more severe), requires inpatient hospitalization for more than 24 hours, causes permanent or significant disability, requires medical or surgical intervention to prevent permanent sequelae, or any of the outcomes listed above.

When the investigator or designee becomes aware that a serious AE has occurred, the Sponsor or designee must be notified immediately by telephone and followed by an e-mailed or faxed written report, regardless of the relationship (or lack thereof) of the AE to the study treatment. The investigator will be notified of the occurrence of serious, unexpected AEs at other study sites. If such AEs are also associated with the use of the study device (i.e., there is a reasonable possibility that the AE may have been caused by the device) and are thus deemed significant new adverse effects or

risks with respect to the investigational device, the investigator must promptly inform the relevant Institutional Review Board.

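### The relatedness scale is stricter about other causes at 'Possibly' than at 'Probably', leaving a gap, and it grades the device only although safety outcome 1 also counts procedure- and therapy-related events

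*Protocol*

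**What the plan says.** Section 2.3 lists as its first safety outcome "Incidence of device-related, procedure-related and therapy- related adverse events". Section 8.4 tabulates adverse events by severity, anticipated status and causality.

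The only graded causality criteria are in Section 7.3.4, headed "Definitions for Criteria of Relatedness of Adverse Events to Device" and worded in terms of product administration. The five levels combine timing, the strength of other explanations and, at some levels, common medical knowledge:

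- *Unrelated*: timing rules out causation, **or** another cause is a strong explanation; alternatively, medical knowledge makes causation implausible.
- *Unlikely*: timing makes causation unlikely, **or** another cause is sufficient; alternatively, medical knowledge makes causation unlikely.
- *Possibly*: timing makes causation "equally likely or not likely, and, other drugs, therapeutic interventions or underlying conditions provide only a low probability explanation" of the event.
- *Probably*: timing makes causation probable, **and** "other drugs, therapeutic interventions or underlying conditions do not provide a sufficient explanation for the observed event".
- *Definitely*: timing makes causation certain, **and** medical knowledge makes it highly probable. Other causes are not mentioned.

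For the three attributions, Section 7.3.1(a) works by example. It states that "Risks of endoscopic placement of the A-Tube, as outlined in Section 7.1.1, are examples of procedure-related adverse events", and it links Section 7.1.2 to device-related events and Sections 7.1.3 and 7.1.4 to therapy-related events.

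**The concern.** A causality scale should tolerate less of a competing explanation as relatedness rises. Here the condition loosens from *Possibly* to *Probably*. The event left without a level is a common type of doubtful event: it might be the device, and something else might account for it but does not clearly do so. The assessor must choose a level whose definition is not met. A choice of *Unlikely* would take the event out of any count that starts at *Possibly*.

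Separately, three incidences are wanted and only one attribution has graded criteria. If procedure- and therapy-relatedness are read from the example lists, similar events may be put in different classes.

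**Working it through.** The plan gives no figure to reproduce, so the check is logical.

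**Step 1: the scale.** Cross five grades of timing with four grades of other cause (none or low; middling but not sufficient; sufficient; strong). Take medical knowledge as neutral, meaning that it neither makes causation implausible or unlikely nor makes it highly probable. The grid is a device for reading the definitions; its cells say nothing about how often events occur.

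| Timing | None or low | Middling | Sufficient | Strong |
|---|---|---|---|---|
| Not possible | Unrelated | Unrelated | Unrelated and Unlikely | Unrelated |
| Unlikely | Unlikely | Unlikely | Unlikely | Unrelated and Unlikely |
| Even odds | Possibly | **no level** | Unlikely | Unrelated |
| Probable | Probably | Probably | Unlikely | Unrelated |
| Certain | see below | see below | Unlikely | Unrelated |

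- *Inversion.* *Possibly* accepts only the first column. *Probably* accepts the first two. The timing condition is in the right order; the other-cause condition is not.
- *Gap.* Even odds with a middling cause is not *Unlikely* (timing is not unlikely and the cause is not sufficient), not *Possibly* (the cause is more than low) and not *Probably* (timing is not probable).
- *Certain timing with a low or middling cause.* Read strictly, these two cells also have no level when medical knowledge is neutral, because *Definitely* needs its support. If certain timing is taken to satisfy probable timing, both fall under *Probably*. I do not rely on them.
- *Double levels.* Two cells meet both *Unrelated* and *Unlikely*. Both levels lie below *Possibly*, so a related count is not affected.

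**Step 2: effect on a count.** Section 7.3.4 sets no cut-off for related, which may properly be left to the analysis plan. Assume *Possibly* or higher. Events with probable timing and a middling cause are related wherever the *Probably* line is drawn, so the inversion by itself moves nothing across the boundary. Only events in the gap can go either way.

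**Step 3: the three attributions.** Compare the lists that Section 7.3.1(a) points to:

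- Infection and bleeding are in both 7.1.1 (procedure) and 7.1.2 (device).
- Discomfort and pain are in 7.1.1 and 7.1.2, and in 7.1.3 when the Connector is attached.
- Indigestion, nausea and vomiting are in both 7.1.1 and 7.1.3 (therapy).

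That is 2 + 2 + 3 = 7 of the 14 risks named in 7.1.1. For these symptoms the list does not settle the class, and 7.3.4 gives criteria only for the device.

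**Step 4: the repaired scale on the same grid.** Assigning *Unrelated* and then *Unlikely* first, as now defined, takes the first two rows and the last two columns. Six cells remain (3 timings × 2 causes). Under the wording proposed in the fix, with a low cause, even odds gives *Possibly*, probable timing gives *Probably*, and certain timing gives *Definitely* if its other conditions hold and *Probably* if not. With a middling cause, all three timings give *Possibly*. Every cell has exactly one level. Probable timing with a middling cause drops from *Probably* to *Possibly* but stays on the related side.

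**The case against.** The case against has real force. Section 7.3.1(a) does assign each risk group to a class and calls the lists examples; one symptom can arise from placement, from the tube or from aspiration, so shared symptoms are not a contradiction. Section 7.4 sets up an independent Safety Adjudication Committee to promote consistent reporting, with duties set out in the Investigators' Brochure. Section 7.3 refers to Appendix K for adverse event guidelines. Neither is shown, and either may add rules. No safety hypothesis is tested on relatedness: the Fisher test in Section 8.4 is on subjects with any adverse event, and trial success rests on the two effectiveness endpoints (Section 2.1).

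This defeats three stronger readings that a reader might infer:

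- *That the three incidences cannot be counted.* They can be, by the example lists and whatever the unseen documents add; what is missing from the protocol text is graded criteria.
- *That an event can be both* Definitely *and* Unrelated *on timing and other cause alone.* *Definitely* also needs medical knowledge to make causation highly probable.
- *That aspiration therapy is left out of causality reporting generally*, because one report asks for "the investigator's assessment of relatedness to the endoscopic procedure or the presence of the A-Tube". That report concerns unanticipated events and deaths, not all adverse events. Hypokalemia, for example, is listed in 7.1.3 and so is classed as therapy-related.

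What stands is the printed wording of 7.3.4. Adjudication or guidance may soften its effect, but the definitions remain out of order and incomplete, and the heading still names only the device.

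**Conclusion.** The point holds as a defect of definition. The other-cause condition is inverted between *Possibly* and *Probably*; one kind of ambiguous event has no level, at the boundary that matters most for a related count; and the graded scale covers one of the three attributions in safety outcome 1. Counts may therefore be classified inconsistently.

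Its size cannot be given from the documents. The share of events in the gap is not stated, and the conclusion that only those events could change sides assumes a cut-off at *Possibly* or higher. A reader might take the remark that "It is normal for subjects to have abdominal discomfort after endoscopic A-tube (or PEG tube) insertion" to mean that nearly all 117 AT subjects would move one class or another to about 100%. The protocol does not say how many subjects would have such discomfort reported as an adverse event, so that does not follow. Nor does an effect on the primary endpoints: Section 8.5 treats dropouts with device-related events as failures, but it also includes other reasons leading to negative outcomes, so the class need not decide the result.

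**What to change.** In Section 7.3.4:

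1. Assess *Unrelated* first, then *Unlikely*, both as now defined, and assign the first one met.
2. Of the remaining events, *Definitely* means that timing is certain, common medical knowledge makes causation highly probable, and no other cause explains the event.
3. *Probably* means that timing is at least probable and other causes are of low probability only, without meeting *Definitely*.
4. *Possibly* means all others: timing about as likely as not, or another cause plausible but not sufficient.
5. State that the scale is applied separately to the endoscopic procedure, the device and aspiration therapy.

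The order in item 1 is essential. If *Possibly* were simply widened to include any plausible but insufficient cause, an event with impossible timing could meet both *Unrelated* and *Possibly*.

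In Section 8.4, tabulate causality by the three classes. Carry the same wording into Appendix K and the adverse event form if they repeat the scale.

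The cost is a few more fields on the adverse event form. One event may count in two classes, and related-event counts may be slightly less favourable because events in the gap become *Possibly*.

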7.3.5 Definitions for "Results" on the AE CRF

- 1. Resolved: No more evidence of the event
- 2. *Improved*: The symptoms associated with the event have become mild or significantly decreased
- 3. *Unchanged*: No reported change in the event
- 4. *Worsened*: The symptoms associated with the event have become significantly worse
- 5. *Permanent Disability*: The subject has lost a specific bodily function
- 6. *Death*: N/A
- 7. *Other*: Result or outcome that does not fit the above definitions and requires written explanation

7.4 Data and Safety Monitoring

Data from the study will be monitored on a continuous basis by the study team (PI, co-investigators, and study research nurse/coordinator). The study team will meet regularly to review subject progress, adverse events (AEs), laboratory values, and any study issues. The local IRB and the Sponsor will be notified of AEs/SAEs as stated in section E3 of this protocol. Information regarding SAEs occurring at any site will be disseminated by the Sponsor to all study sites and the information reported to the IRB. If, at any time during the study, an unanticipated significant risk to study subjects is identified, study recruitment and/or the study intervention may be stopped until such

risk has been satisfactorily resolved or corrective action taken and all study documents updated, as needed. The need to stop or interrupt study activity will be determined by the Sponsor and PI.

To ensure consistency in reporting adverse events and to meet the ethical responsibilities and standards for research subjects, a Safety Adjudication Committee (SAC) has been formed. The SAC is composed of a group of independent physicians who have no financial interest in the Sponsor (or a competitor to Sponsor) and who have expertise in gastrostomy tubes, metabolism, and obesity. The responsibilities of this committee are described in the Investigators' Brochure.

Confidentiality. All of the data will be treated confidentially and the subjects' names and identities will not be disclosed in any published reports. Subjects are assigned a study specific identifying number upon entry to the study, after which all medical information is referenced by this number. Clinic records are maintained in locked file cabinets within a locked room.

8.0 Statistical Analyses

8.1 Sample Size

Based on weight loss data and drop-out data from the prior trials involving aspiration therapy, a study size of 175 subjects, with 2:1 randomization, should adequately power the trial to demonstrate efficacy.

8.1.1 Efficacy Endpoints

The first effectiveness primary endpoint is the mean percent excess weight loss (%EWL) at 52-weeks. The hypothesis for the first primary effectiveness endpoint is that the difference in the mean percent excess weight loss (%EWL) at 52-weeks for the Aspiration Therapy (AT) group and Control group is at least 10%. %EWL is defined as absolute weight loss divided by baseline excess weight and multiplied by 100. Excess weight will be determined from ideal body weights based on a BMI=25 kg/m².

The second effectiveness primary endpoint is that at least 50% of the AT group at 52-weeks realizes a %EWL \geq 25%.

Sections 8.51 and 8.52 provide analysis of the sample size to meet co-primary endpoint #1 and #2, respectively with a power of 90% for each endpoint.

Since these endpoints are co-primary, the sample size is determined by the largest sample sizes required of the two primary endpoints. Co-primary endpoint #1 requires a sample size of 87 subjects (59 AT/ 29) to have a superiority margin of 10% EWL with a power of 90%, assuming an observed difference of 25% EWL and a standard deviation of both groups of 20%. Co-primary endpoint #2 requires a sample size of 99 AT subjects to realize that at least 50% of the AT groups realize >25% EWL at 52 weeks with a power of 90%, assuming an observed rate of 66% and a standard deviation of 20% of the AT group.

Co-primary endpoint #2 requires the largest sample sizes of the two primary endpoints, hence, not accounting for subject drop-out, a total of 150 subjects are needed in a 2:1 randomization (100 AT + 50 Control).

Since the primary analysis will be based on an ITT analysis using multiple imputations to estimate the missing values, the importance of over enrolling to have the exact number of evaluable patients has been lessened. However, to mitigate the effect of the imputation methodology on the control group, an over enrollment of ~15% for both groups is being proposed for a total enrollment size of 175 subjects (117 AT/58 Control).

8.1.2 Discussion on Drop-out Rate and Standard Deviation.

As 9% of the AT subjects (1 out of 11) in the Feasibility Study did not complete 52-weeks, we believe a 10% drop-out rate of the AT subjects for the Pivotal Study is a reasonable assumption. An over-enrollment of 15% (e.g., 117 AT subject versus 99 required) should readily accommodate the anticipated drop-out rate.

A lower drop-out rate for the Controls (20%) is being assumed for the Pivotal Study than what was experienced in the Feasibility Study (43%; 3 out of 7 subjects). Although 20% is still higher drop-out rate than many drug studies, we believe that this drop-out rate for Controls should be anticipated given the disappointment some of the Controls will have in not being chosen as an AT subject. Data from a recently published article that compared bariatric surgery with intensive medical therapy in obese subjects with diabetes

support our estimate of a 20% drop-out rate. In that study, subjects were randomized into three equal arms: intensive medical therapy, gastric bypass, and sleeve gastrectomy^{62,} and the drop-out rate for the intensive medical therapy arm was 18% compared to 4% and 0% for the other two arms, respectively.

A standard deviation of approximately 25% in %EWL at 52-weeks was seen in both the AT and control groups. In the larger sample size associated with the Pivotal Trial, the extreme values will have a lessened impact on the variability of the observed responses. Hence, a reduction in standard deviation from 25%, as experienced in the Feasibility Trial, to an assumed 20% for the Pivotal Trial is realistic. The assumption of a 20% standard deviation is consistent with other obesity device weight loss studies. The Lap-Band PMA study had a 19% standard deviation at 1 year.⁶³ Similarly, the Realize Band study had nearly an 18% standard deviation at 1 year.⁶⁴

